## 7.3. Statistical Analysis of Biomarker Outcomes

The following analysis will be performed based on the Biomarker Population.

Week 52 samples taken after the first day of the open-label treatment phase will not be used in the analysis.

Since from protocol version 5 on, the control group had occasional spiking with 4mg MTC with an average frequency of twice per week, it is therefore of interest to test not only the doses of HMTM compared to control, but also to a subpopulation of control that showed lowest predicted concentrations of parent MT at Week 52. A threshold of  $\leq 0.1$  ng/mL for predicted Week 52 steady-state ( $C_{max,ss}$ ) parent MT concentration will be used to define the lowest parent MT group. In the analysis output the control group will be presented as "MTC 8 mg/week".

The actual received treatment and the actual (verified) values of the randomization stratification variables will be used in the analysis.

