In the continued development of LMTM, the efficacy of LMTM is to be confirmed in a placebo-controlled study at a dose of 16 mg/day. A population PK model was developed based on Study TRx-237-036 and applied to plasma concentrations from the Phase 3 studies. Using per-patient peak steady-state plasma concentration ( $C_{max,ss}$ ) estimates, concentration-response analyses for ADAS-cog11 decline over 65 weeks were performed and a  $C_{max,ss}$  threshold of 0.373 ng/mL was identified. The clearance of parent MT/LMT is most significantly associated with renal function, suggesting that the most important predictor of whether or not a subject achieves a parent MT/LMT  $C_{max,ss}$  above the threshold is creatinine clearance. At a dose of 8 mg/day, approximately 60% of subjects with normal renal function

would be expected to have plasma concentrations above the threshold, whereas at a dose of 16 mg/day, all subjects would.

The co-primary endpoints are ADAS-cog11 and ADCS-ADL23, consistent with trials in subjects with mild to moderate AD. Based on the prior studies, a 12-month duration is deemed sufficient to demonstrate superiority to placebo. To address concerns regarding inadvertent unblinding due to urinary discoloration, subjects randomized to placebo may receive a 4-mg MTC tablet as one of the four tablets to be taken daily. As subjects with early AD (also referred to as prodromal AD/mild cognitive impairment due to AD [MCI-AD]) are also included in the study, F-FDG-PET and clinical composite scales are included as sensitive endpoints for this subset of subjects.

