### **12.3 Randomization**

Subjects will be randomized to one of three study regimens described in Section 12.2: LMTM 16 mg/day, LMTM 8 mg/day, or placebo (4:1:4, at the study level). Randomization will be stratified according to severity (three levels: MMSE 16-19, 20-25, or 26-27) at study level for those randomized to Protocol Version 5.0 and above, prior use of standard AD treatment (two levels: AChEI/memantine or none), and region (two levels: North America or Europe).

Enrollment will be such that subjects are assigned to the MMSE severity groups based on screening MMSE score with a target of approximately 2:3:1 (MMSE 16-19, MMSE 20-25, and MMSE 26-27, respectively) for those randomized to Protocol Version 5.0 and above; to achieve this target, enrollment will be monitored and controlled at the site level for high recruiting sites and capped as needed at the study level.

Randomization, stratification, and enrollment cap requirements will be controlled by a web-based RTSM system.

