In the continued development of HMTM, 16 mg/day has been chosen as the primary target dose. This was based on a population PK-response model that was applied to data from the earlier Phase 3 studies. The clearance of parent Methylthioninium (MT) is most significantly associated with renal function, suggesting that the most important predictor of whether or not a subject achieves a parent MT Cmax,ss above the threshold is creatinine clearance. At a dose of 8 mg/day, approximately 60% of subjects would be expected to have plasma concentrations above the threshold concentration that was identified with pharmacologic activity whereas at a dose of 16 mg/day, all subjects would. In order to provide some degree of urinary discoloration in what was originally a "true" placebo control group, a small amount of methylthioninium chloride (MTC), 4 mg, was introduced to placebo treatment kits (one tablet on two intermittent occasions twice per week, i.e., 8 mg/week). This amount of MTC had been anticipated to be without activity, consistent with results of a prior Phase 2 trial and estimated plasma

Sponsor:	TauRx Therapeutics Ltd.		
Protocol:	TRx-237-039		
Document Version No.:	3.0	Document Date:	07-JUN-2023

---

half-life. For this reason, this treatment arm is referred to herein (and in tables, listings, and figures) as “control” rather than “placebo”.

This document describes the plan for the full statistical analyses and reporting of study TRx-237-039, which in its current version is a randomized, double-blind, controlled, three-arm, 12-month, safety and efficacy study of HMTM monotherapy in subjects with AD followed by a 12-month open-label treatment. Results of the analyses described in this Statistical Analysis Plan (SAP) will be included in the Clinical Study Report (CSR).

The planned analyses identified in this SAP will be included in regulatory submissions and future manuscripts. Any post-hoc or unplanned analyses performed to provide results for inclusion in the CSR but not identified in this prospective SAP, will be clearly identified in the CSR.

This SAP is primarily based on the protocol version 7.0 from 28-JUL-2021 and version 7.0 UK from 19-AUG-2021. Key decisions based on earlier versions are acknowledged where appropriate.

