### 7.3.2. Primary Outcomes

For each of the primary exploratory biomarkers P-tau181 and NfL, an ANCOVA will be used to analyze the change from Baseline at Week 52 visit within each treatment group (HMTM 16 mg/day, HMTM 8 mg/day, and control). In this ANCOVA, the change from Baseline at Week 52 will be compared pairwise

Sponsor:	TauRx Therapeutics Ltd.		
Protocol:	TRx-237-039		
Document Version No.:	3.0	Document Date:	07-JUN-2023

for these three treatment groups. The ANCOVA model will include the randomization stratification variables (see Section 2.6) as fixed factors, the respective efficacy Baseline value as covariate, and the treatment indicator; with the Kenward and Roger method used for calculating the denominator degrees of freedom for the tests of fixed effects. One table will present the LSM for the change from Baseline and the pairwise treatment contrasts at Week 52, and one table will present the p-values of the type 3 tests of the fixed effects along with the estimates of the factors and covariates which are included in the model.

In a sensitivity analysis, subject's age and sex, as well as *ApoE4* carrier status and plasma sample age will be added as further covariates in the primary model. The plasma sample age (of the Week 52 sample) is the difference between the day when the sample was analyzed and the day when the sample was taken + 1. For NfL: a mid-point sample analysis date will be applied, to calculate the plasma sample age. In a second and third sensitivity analysis, Baseline values of MRI whole brain volume and F-FDG-PET temporal lobe glucose uptake normalized to pons will be included separately as covariates as well. Factors with a p-value of 0.2 or smaller will be investigated further upon request.

In addition, this primary model will be repeated with the control group being restricted to the subpopulation with lowest parent MT.

This primary model will be repeated (not including the sensitivity analyses and not including the analysis with respect to the lowest parent MT control group) for the subgroups of the stratification variables region, prior use of AChEI and/or memantine, and Baseline MMSE severity (16-19, and 20-27). For the Baseline MMSE severity, the additional split into the subgroups of scores 16-21, and 22-27 will be done as well. This analysis will also be repeated for the verified AD diagnosis subgroups MCI-AD and probable AD.

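### The low-drug-level biomarker repeat restricts only the control arm, so it is not a randomized contrast and is open to confounding, with no adjustment for renal function

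*SAP*

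**What the plan says.** - **Comparator.** SAP 7.3 wants HMTM tested against control as a whole and also against "a subpopulation of control that showed lowest predicted concentrations of parent MT at Week 52". A predicted Week 52 steady-state Cmax of at most 0.1 ng/mL for "parent MT concentration will be used to define the lowest parent MT group".
- **Model.** SAP 7.3.2: "this primary model will be repeated with the control group being restricted to the subpopulation with lowest parent MT". No matching restriction is placed on HMTM 16 mg/day or 8 mg/day.
- **Covariates.** "The ANCOVA model will include the randomization stratification variables (see Section 2.6) as fixed factors, the respective efficacy Baseline value as covariate", plus treatment. SAP 2.6 lists the strata as MMSE severity, prior AChEI/memantine use and region.
- **Sensitivity models.** In the first, age, sex, ApoE4 "carrier status and plasma sample age will be added as further covariates in the primary model". The others add baseline whole brain volume or FDG-PET. None is stated to apply to the low-level repeat.
- **What drives drug level.** Protocol 8.2: "The clearance of parent MT/LMT is most significantly associated with renal function". SAP 1.1: "the most important predictor of whether or not a subject achieves a parent MT Cmax,ss above the threshold is creatinine clearance".
- **Status.** SAP 7 calls these analyses exploratory, with nominal p-values and no multiplicity correction.
- **Population.** SAP 7.2 takes version 5.0+ completers without off-treatment subjects. It also admits subjects randomized under earlier versions who completed the phase and have Week 52 biomarker data.

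**The concern.** The full-control comparison is between randomized groups, apart from the restriction to completers. The repeat is not: every eligible HMTM subject is compared with controls kept because of a level predicted a year after randomization. If the level depends on renal function, the kept controls will tend to have better renal function than the HMTM arm. If renal function also relates to 52-week change in P-tau181 or NfL, part of the estimated difference is not a drug effect.

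The planned output would not reveal this. SAP 7.3.1 summarizes biomarkers, scales and imaging for the low-level group, but not creatinine clearance or age. Nominal p-values deal openly with multiplicity; they say nothing about bias. The result could still matter: SAP 1.1 expects planned analyses to enter submissions and manuscripts, and SAP 7.4 makes an apparent benefit on any biomarker the trigger for further sample analysis.

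**Working it through.** The plan gives no sample size, power or error rate for this contrast, so there is no figure to reproduce.

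**1. Is renal function adjusted for anywhere?** I read the models in SAP 7.3.2 and 7.3.5. The terms are the strata, baseline biomarker, treatment, age, sex, ApoE4, sample age, brain volume and FDG-PET. Creatinine clearance is in none of them. It is collected at baseline (Protocol 15.1) and tabulated for other populations (SAP 5.7). Only values below 30 mL/min are excluded (Protocol 11.2), so mild and moderate impairment can be present.

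**2. Does the renal link carry over to control dosing?** The statements in Protocol 8.2 and SAP 1.1 come from HMTM data and a threshold that the protocol gives as 0.373 ng/mL. Controls take one 4 mg MTC tablet twice a week (SAP 5.12.1), a mean interval of 168/2 = 84 h. Protocol 8.1.3.1 gives single-dose mean half-lives of 15.7 h (healthy controls), 24.4 h (mild impairment) and 29.3 h (moderate). One-compartment accumulation is 1/(1 − 2^(−τ/t½)):

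| Interval τ | 15.7 h | 24.4 h | 29.3 h | Moderate/normal |
|---|---|---|---|---|
| 12 h | 2.43 | 3.46 | 4.05 | 1.66 |
| 84 h | 1.03 | 1.10 | 1.16 | 1.13 |

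The gradient keeps its direction but is much smaller under MTC. This assumes that MTC behaves like LMTM.

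**3. Where does the cut fall?** Protocol 8.1.3.1 reports a mean Cmax of 0.1 ng/mL after one 4 mg LMTM dose, numerically equal to the cut. On the same assumption, the cut lies near the middle of MTC-dosed controls, where differences between subjects decide who is kept.

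**4. Illustration of size, including no bias.** Assumptions, none of them a property of this contrast stated in the documents:
- 160 HMTM subjects, and a share f = 0.5 of 160 controls kept, so 80.
- r is the size of the correlation between level and renal function.
- b is the correlation between renal function and biomarker change.
- The true drug effect is zero.

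Formulas: renal gap = r·φ(z_f)/f = r × 0.399/0.5 = 0.798r SD. Bias = b × gap. SE = √(1/160 + 1/80) = 0.137 SD. Two-sided error = Φ(−1.96 − bias/SE) + 1 − Φ(1.96 − bias/SE).

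| b | r = 0.3 (gap 0.24 SD) | r = 0.5 (gap 0.40 SD) | r = 0.7 (gap 0.56 SD) |
|---|---|---|---|
| 0 | 5.0% | 5.0% | 5.0% |
| 0.1 | 5.4% | 6.0% | 6.9% |
| 0.2 | 6.4% | 9.0% | 12.9% |
| 0.3 | 8.2% | 14.1% | 23.1% |

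Worked cell (r = 0.5, b = 0.2): bias = 0.2 × 0.399 = 0.080 SD; 0.080/0.137 = 0.58; error 9.0%. In a simulation of this set-up (5,000 runs per setting, b = 0, 0.2 and 0.3), adding baseline renal function brought the bias to within 0.003 SD of zero and the error to 4.6–5.3%. That simulation has renal function as the only confounder.

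**5. Is renal function the only route?** No. Table 1 of the SAP shows MMSE 20–25 or 20–27 before version 5.0, against 16–27 afterwards. SAP 4.6 recognizes placebo-only controls and controls who moved from placebo to MTC. Any placebo-only control in the Biomarker Population would be expected to fall under the cut whatever their renal function.

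**The case against.** The other side has real force.

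- **Exploratory status.** The SAP says so plainly, keeps the full-control comparison as the main biomarker analysis, and openly calls the subset a subpopulation. This stands, and it limits the point to a minor improvement.
- **No shown link to the outcome.** Confounding needs renal function to relate to change in P-tau181 or NfL, given baseline. The documents report no such association, and the model already adjusts for the baseline biomarker. This stands: the contrast is open to confounding, which is less than saying that it is confounded.
- **Weak link to the selection variable.** Protocol 8.1.3.1 reports a single-dose Cmax effect only in severe renal impairment, puts renal clearance at 13% of apparent clearance in healthy volunteers, and shows 2.1- to 3.2-fold higher Cmax in mild to moderate hepatic impairment. Much of the variation in level may not be renal. This also stands. It weakens the renal route but does not make a comparator selected on drug level a randomized one.
- **Tablet intake.** A reader might infer that the subset also selects controls who took fewer tablets. The documents do not support that. The version 5.0+ Biomarker Population is completers without off-treatment subjects, and how Cmax,ss is predicted belongs to a separate pharmacokinetic SAP.

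**Conclusion.** The point holds as a minor one. The low-level repeat is a non-randomized comparison, open to confounding by determinants of drug level. Renal function is the determinant that the documents themselves put first, and no model in the section adjusts for it. The protocol-version mix is a second route.

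The size is unknown. In the illustration, error runs from 5.0% with no renal–biomarker association to 23.1% at the most adverse inputs; those inputs are assumed, and the direction of any bias is not known. A reader might take such figures as an established inflation of error, and the documents do not support that. A reader might also suspect that the subset was picked from results, because SAP 10 places version 3.0 after partial unblinding. The documents do not show that either; they do not say when the subset was first specified. The trial's primary analyses are unaffected.

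**What to change.** In SAP 7.3.2, for the low-level repeat only:

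1. Add baseline creatinine clearance and age to the ANCOVA.
2. Add an indicator for randomization before version 5.0 versus under version 5.0 or later, or restrict the repeat to version 5.0+ subjects. A renal covariate alone does not deal with the protocol-version mix.
3. Tabulate creatinine clearance and age for the low-level subset beside each randomized arm.
4. Label the contrast non-randomized in the table and figure titles.

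Cutting both arms at the same creatinine clearance is not a substitute, because it would not by itself isolate the low-level controls, who are the stated interest.

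The cost is SAP wording and variables already in the database. It uses a few degrees of freedom, loses any subject missing a covariate, and puts a less favourable label on one exploratory result. Adjustment reduces the risk but does not restore randomization, so the label is needed in any case.

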### 7.3.1. Summary Statistics

The Baseline and Week 52 visit value of each biomarker to be analyzed, of the scales (ADAS-cog13, ADAS-cog11, and ADCS-ADL23) and MRI and F-FDG-PET parameter as mentioned in Section 7.3.3, will be analyzed descriptively (n, mean, median, lower quartile (Q1), upper quartile (Q3), standard deviation, standard error, minimum and maximum values) and will be presented by treatment group, and for the lowest parent MT group as a separate group, and by Baseline MMSE score subgroups.

Baseline MMSE score subgroups are defined as 16-19, and 20-27. An additional split of the scores into 16-21, and 22-27 will be investigated. Also, a split into the verified AD diagnosis subgroups MCI-AD and probable AD will be provided as per the information provided in the Diagnostic Verification form.

The descriptive analysis of the scales and parameters will be repeated, since the analysis population is different to the double-blind treatment phase populations.

### 7.3.2. Primary Outcomes

For each of the primary exploratory biomarkers P-tau181 and NfL, an ANCOVA will be used to analyze the change from Baseline at Week 52 visit within each treatment group (HMTM 16 mg/day, HMTM 8 mg/day, and control). In this ANCOVA, the change from Baseline at Week 52 will be compared pairwise

Sponsor:	TauRx Therapeutics Ltd.		
Protocol:	TRx-237-039		
Document Version No.:	3.0	Document Date:	07-JUN-2023

for these three treatment groups. The ANCOVA model will include the randomization stratification variables (see Section 2.6) as fixed factors, the respective efficacy Baseline value as covariate, and the treatment indicator; with the Kenward and Roger method used for calculating the denominator degrees of freedom for the tests of fixed effects. One table will present the LSM for the change from Baseline and the pairwise treatment contrasts at Week 52, and one table will present the p-values of the type 3 tests of the fixed effects along with the estimates of the factors and covariates which are included in the model.

In a sensitivity analysis, subject's age and sex, as well as *ApoE4* carrier status and plasma sample age will be added as further covariates in the primary model. The plasma sample age (of the Week 52 sample) is the difference between the day when the sample was analyzed and the day when the sample was taken + 1. For NfL: a mid-point sample analysis date will be applied, to calculate the plasma sample age. In a second and third sensitivity analysis, Baseline values of MRI whole brain volume and F-FDG-PET temporal lobe glucose uptake normalized to pons will be included separately as covariates as well. Factors with a p-value of 0.2 or smaller will be investigated further upon request.

In addition, this primary model will be repeated with the control group being restricted to the subpopulation with lowest parent MT.

This primary model will be repeated (not including the sensitivity analyses and not including the analysis with respect to the lowest parent MT control group) for the subgroups of the stratification variables region, prior use of AChEI and/or memantine, and Baseline MMSE severity (16-19, and 20-27). For the Baseline MMSE severity, the additional split into the subgroups of scores 16-21, and 22-27 will be done as well. This analysis will also be repeated for the verified AD diagnosis subgroups MCI-AD and probable AD.

It is of interest to analyze the correlation between change in NfL and ADAS-cog11 accounting for baseline values of NfL and potentially treatment allocation; to address this: the ADAS-cog11 change from Baseline at Week 52 will be added as a covariate to a simplified ANCOVA model, additionally only accounting for baseline NfL. In an additional model the ADAS-cog11 change from Baseline at Week 104 will be added as a covariate instead. These analyses will be repeated for the verified AD diagnosis subgroups MCI-AD and probable AD, and further repeated replacing ADAS-cog11 by ADCS-ADL23 and MRI whole brain volume (separately). More advanced versions of this simple model relying on interaction terms or additional covariates might be explored. Analyses targeting a more direct evaluation of the correlation might be explored still accounting for potential covariates. This might be repeated for other potential biomarkers.

It is also of interest to analyze the correlation between baseline values of NfL and ADAS-cog11 accounting for the randomization stratification variables (see Section 2.6) in an ANCOVA model with NfL Baseline being the independent variable and ADAS-cog11 Baseline the dependent variable. This analysis will be repeated for the verified AD diagnosis subgroups MCI-AD and probable AD, and further repeated replacing ADAS-cog11 by ADCS-ADL23 and MRI whole brain volume (separately).

Sponsor:	TauRx Therapeutics Ltd.		
Protocol:	TRx-237-039		
Document Version No.:	3.0	Document Date:	07-JUN-2023

Sample SAS code (will be fully validated at the analysis stage):

```

PROC MIXED DATA=dataset METHOD=REML COVTEST;
  CLASS subject treatment(REF='Control') severity(REF='16-19') region(REF='Europe')
  prioruse(REF='None'); /*additional MMSE split: severity(REF='16-21'); by diagnostic criterion:
  diagnostic(REF='probable AD')*/
  MODEL diff = treatment severity region prioruse scorebl / SOLUTION CL DDFM=
  KENWARDROGER; /*diff: change from Baseline*/
  LSMEANS treatment / CL;
  LSMESTIMATE treatment "HMTM 16 vs. Control" 1 0 -1 / CL; /*Pairwise treatment
  comparison*/
  LSMESTIMATE treatment "HMTM 8 vs. Control" 0 1 -1 / CL;
  LSMESTIMATE treatment "HMTM 16 vs. HMTM 8" 1 -1 0 / CL;
  ODS OUTPUT LSMeans SolutionF Tests3;
  RUN;

```

